#### 8.2. Definition of trial populations included in the analysis

- The efficacy analyses will be performed on the PPS(Per protocol set), defined as all randomized subjects by their assigned treatment arms.
- The PPS(Per protocol set) will be defined as subjects receiving randomized treatment, who meets entry criteria, have not permanently discontinued treatment administration and had no major protocol deviation
- Additionally, efficacy analyses will be performed on a FAS(Full Analysis Set).
- All safety analyses will be performed on the Safety Set, defined as all patients who
  received at least one dose of the treatment.
- Tests of normality will be performed to evaluate the data distribution. Test group of continuous variables will be compared to the placebo group using Independent T-

test, analysis of covariance, and the Wilcoxon rank-sum test. Comparison between groups according to changes in time will be analyzed using Paired T-test. Categorical data will be analyzed using the chi-square test or Fisher's exact test. A two-sided test will be considered significant when the p value <0.05.

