#### 4. Randomization

A random number will be assigned during visit 1 (week 0) in the order in which the subject is enrolled according to the inclusion and exclusion criteria. Subjects will be assigned to the study group, based on a random list prepared by a third party independent of the study before the study begins. Study participants will be allocated to the control group, and the test group (KeranatTM) at a 1:1 ratio using a block randomization method. The study will be double-blind and group assignments will not be disclosed to investigators or subjects until the end of the study.

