### 8. Statistical Analysis Plan

The Statistical Analysis Plan will be written after the protocol finalization and definitely finalized before breaking the blind mode, prior to the first database lock. These specifications will detail the implementation of all statistical analyzes planned according to the main features reported in the protocol.

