#### 8.1. Sample size determination

This study hypothesizes that the use of Keranat™ will improve hair health. Therefore, a primary comparison will be conducted between the placebo arm and the test arm(Keranat™).

To calculate the number of test subjects, based on a 24-week intake study similar to this clinical trial, the change in hair count per unit area (Mean  $\pm$  SD) of the test group was assumed to be 16.9  $\pm$  15.6 and the control group was 4.5  $\pm$  14.9. (d=12.4)

- (1)  $H_0: \mu t = \mu c \text{ VS } H_1: \mu t \neq \mu c$
- (2) At the 5% significance level, the type 2 error is 0.2, maintaining 95% power. ( $\alpha$  = 0.05,  $\beta$  = 0.2, statistical power =95%)
- (3) test group : placebo group = 1:1(k=1)
- (4) Calculation program: G\*power 3.1.9.2

As a result of calculating the number of subjects using G\*power 3.1.9.2, the number of subjects was calculated to be 41 per group and a total of 82. After considering the dropout rate of 20%, the number of subjects was calculated to be 50 per group and a total of 100.

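### Section 8.2 puts the efficacy analyses on a per-protocol set that it defines in two incompatible ways and never defines the full analysis set, so the lead analysis population cannot be determined as written.

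*Combined protocol and SAP*

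**What the plan says.** Section 8.2 opens with: "The efficacy analyses will be performed on the PPS(Per protocol set), defined as all randomized subjects by their assigned treatment arms". The second bullet of the same section defines the PPS again, as "subjects receiving randomized treatment, who meets entry criteria, have not permanently discontinued treatment administration and had no major protocol deviation". The third reads "Additionally, efficacy analyses will be performed on a FAS(Full Analysis Set"; no definition of the FAS follows there or anywhere else. The Safety Set is defined once and is not in dispute.

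Section 8.1 says that "a primary comparison will be conducted between the placebo arm and the test arm". This names the arms but no analysis set. Section 2.2.1 lists two primary endpoints, the changes in hair elasticity and hair gloss from baseline to week 24, again without a set.

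Section 8 defers detail to a separate SAP, which will "detail the implementation of all statistical analyzes planned according to the main features reported in the protocol" and is to be "definitely finalized before breaking the blind mode, prior to the first database lock". That SAP is not among the documents.

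**The concern.** The first two bullets cannot both be followed. Read literally, the first keeps every randomised subject in the assigned arm and so preserves the randomised comparison. It looks like a full-analysis definition under the wrong label, but nothing confirms that. The second removes subjects because of events after randomisation.

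The choice can change who is counted for both primary endpoints. If the second bullet governs, the main superiority test is made on a selected subset. Its result is biased if the link between exclusion and outcome differs by arm. If the two analyses disagree, the plan gives no rule for which one decides.

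**Working it through.** **1. The definitions side by side (Section 8.2)**

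| Randomised subject | First bullet | Second bullet |
|---|---|---|
| Treated, eligible, completes, no major deviation | in | in |
| Permanently stops treatment | in | out |
| Found not to meet entry criteria | in | out |
| Major protocol deviation | in | out |
| Never received treatment | in | out |

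The sets coincide only if nobody falls in the last four rows.

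**2. The plan's own figure (Section 8.1)**

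Inputs are changes of 16.9 ± 15.6 and 4.5 ± 14.9 in hair count per unit area, two-sided alpha 0.05 and power 95%.
- Pooled SD = √((15.6² + 14.9²)/2) = 15.254.
- Standardised difference = 12.4/15.254 = 0.813.
- The noncentral t gives 41 per group (power 95.3%), which reproduces the plan. Section 8.1 also states a type 2 error of 0.2; that would give 25 per group, so 95% was the power used.

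Section 8.1 continues: "After considering the dropout rate of 20%, the number of subjects was calculated to be 50 per group and a total of 100". That 20% is dropout, which affects either set. The documents do not say how many subjects would be measurable at week 24 yet excluded by the PPS rule.

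**3. Type I error if the second bullet governs (illustration, all inputs assumed)**

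No true effect, two-sided 5% t-test, and 40 measurable per arm (50 × 0.8, dropout taken as random). Each subject has a latent score with correlation r to outcome and is excluded if the score falls below a population cut-off. A 10% cut-off excludes about 4 per arm.

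Bias in SD units = (r_test − r_placebo) × φ(1.2816)/0.9 = 0.195 × (r_test − r_placebo).

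| r test / r placebo | Bias (SD) | About 2 excluded | About 4 excluded | About 6 excluded |
|---|---|---|---|---|
| equal | 0.00 | 5.0% | 5.0% | 5.0% |
| 0.3 / 0.2 | 0.02 | 5.0% | 5.1% | 5.2% |
| 0.5 / 0.2 | 0.06 | 5.3% | 5.7% | 6.3% |
| 0.3 / 0 | 0.06 | 5.3% | 5.7% | 6.3% |
| 0.5 / 0 | 0.10 | 5.7% | 7.0% | 8.8% |

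The last three columns are simulated type I error. The bias column is for about 4 excluded. Swapping the arms reverses its sign.

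**4. The same mechanism applied to dropout**

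A FAS restricted to subjects with a week-24 value is also selected after randomisation. With 50 per arm and the 20% dropout following the mechanism of step 3, the bias factor is φ(0.8416)/0.8 = 0.350.
- 0.5 / 0: type I error 12.4%, bias 0.17 SD.
- 0.3 / 0: type I error 7.5%, bias 0.10 SD.
- Equal selection: about 5%, no bias.

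So renaming the set is not enough. By the Section 6 schedule, elasticity is measured only at V1 and V5, so a subject who drops out has no intermediate value. Gloss is also measured at V2 and V3.

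**5. Power cost of an all-randomised primary set**

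Assume that a fraction f is excluded in each arm, that excluded test-arm subjects show the control mean, and that all 50 per arm are observed. The all-randomised difference is 12.4(1 − f). Test-arm variance becomes (1 − f)15.6² + f·14.9² + f(1 − f)12.4². At f = 0.2 that is 194.7 + 44.4 + 24.6 = 263.7, so the SD is √((263.7 + 222.0)/2) = 15.58.

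| f | PPS per arm | PPS power | All-randomised difference | All-randomised power |
|---|---|---|---|---|
| 10% | 45 | 96.8% | 11.2 | 94.7% |
| 20% | 40 | 94.8% | 9.9 | 88.3% |
| 30% | 35 | 91.8% | 8.7 | 78.3% |

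Keeping the SD at 15.254 gives 89.6% instead of 88.3% at f = 20%.

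**The case against.** **The plan does rank the sets.** The efficacy analyses are on the PPS and the FAS is additional, so the PPS leads. This stands as an implication. It does not settle the matter, because the label PPS covers two different sets and no explicit primary label is given.

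**The SAP may resolve it.** This also stands. A reader might infer that the SAP must inherit the conflict because it follows the protocol's main features. The documents do not support that: the SAP is written later and could state the set clearly. Equally, nothing available shows that it does.

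**Blinding limits the harm.** Section 4 says that "group assignments will not be disclosed to investigators or subjects until the end of the study", and the SAP is to be final before unblinding. Together these restrict choosing a set after results by arm are seen, and double-blinding makes differential exclusion less likely when there is no effect. Neither says who is in the PPS or which result decides.

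**The all-randomised primary set is a second change.** It reverses the order implied in Section 8.2 and goes beyond reconciling the definitions. That is fair. The reason for it is that the hypothesis in Section 8.1 is one of superiority, for which a comparison of groups as randomised is the safer basis.

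**Conclusion.** The point holds as a defect of definition. The set carrying the efficacy analyses has two incompatible memberships, the FAS has none, and no rule covers disagreement between them. It must be fixed because the instruction cannot be carried out as written.

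A reader might infer that the primary result will be biased or its type I error inflated. The documents do not support that. It needs the restrictive bullet to govern and exclusion to relate to outcome differently by arm. Under the assumed inputs, type I error is about 5% with equal selection, about 5% to 7% with 4 excluded per arm, and up to about 9% with 6 and strong selection in one arm only. The correlations and exclusion counts are assumptions; nothing shows which case applies, and the bias could favour either arm.

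**What to change.** In Section 8.2, replace the first bullet with: *The primary efficacy analysis will be performed on the FAS, defined as all randomised subjects analysed by assigned arm.* Keep the second bullet as the only PPS definition and label the PPS analysis supportive.

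Carry the same text into the SAP before unblinding, with a stated way of handling randomised subjects who have no week-24 value. The rule must work for elasticity, where only a baseline value would exist, as well as for gloss.

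The cost is wording plus that missing-data rule; no extra subjects, visits or measurements are needed. The downside is dilution by non-adherent subjects. Under the assumptions in step 5 of the working, it is small at 10% excluded (power about 97% for the PPS against 95% for the FAS) but not at 20% (about 95% against 88% to 90%).

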#### 2.2. Trial Endpoints

### 2.2.1. Primary Endpoints

- The change of hair elasticity: Change of the week 24 from baseline
- The change of hair gloss: Change of the week 24 from baseline

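### The FAS is undefined and no missing-data method is stated, so with 20% dropout the week-24 tests default to subjects with a V5 value and leave weeks 8 and 16 gloss unused

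*Combined protocol and SAP*

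**What the plan says.** Section 8.2 gives the main efficacy set two meanings. The first bullet reads "The efficacy analyses will be performed on the PPS(Per protocol set), defined as all randomized subjects by their assigned treatment arms". The second limits the same set to treated subjects who meet the entry criteria, "have not permanently discontinued treatment administration and had no major protocol deviation". The FAS then appears once, as an extra: "Additionally, efficacy analyses will be performed on a FAS(Full Analysis Set"). No membership rule follows.

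For continuous variables, the arms are to be compared with an independent t-"test, analysis of covariance, and the Wilcoxon rank-sum test". The only other provisions are a paired t-test ("Comparison between groups according to changes in time will be analyzed using Paired T-test") and tests for categorical data ("Categorical data will be analyzed using the chi-square test or Fisher's exact test"). The document contains no imputation rule, no longitudinal model and no missing-data sensitivity analysis.

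Section 2.2.1 defines both primary endpoints as week-24 change, for example "The change of hair elasticity: Change of the week 24 from baseline"; gloss is worded the same way. The schedule in section 6 has gloss at screening, V1 (day 0), V2 (week 8), V3 (week 16) and V5 (week 24). It has elasticity at V1 and V5 only. Section 8.1 allows for losses ("After considering the dropout rate of 20" per cent). Section 8 leaves implementation detail to a SAP that will be written later and finalised before unblinding.

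**The concern.** A t-test on change, an ANCOVA on the week-24 value or change, and a rank-sum test on change each use one outcome per subject, and that outcome needs a V5 measurement. With nothing said about missing values, a programmer following section 8.2 would drop every subject without V5 from the FAS analysis as well as from the PPS analysis. The analysis that should show whether the result survives selective dropout would then be exposed to it too.

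For gloss this is avoidable. A subject who leaves after week 16 has given a baseline and two on-study values, and these carry information about the missing week-24 value. As written, they contribute nothing to the week-24 gloss comparison. At stake is a modest bias in a primary result if the reasons for leaving differ between arms. The open definitions also leave room to choose the set and the test after data are seen.

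**Working it through.** **1. The plan's own numbers (section 8.1).** Inputs are changes of 16.9 (SD 15.6) and 4.5 (SD 14.9), two-sided alpha 0.05, 1:1 allocation. Pooled SD = √((15.6² + 14.9²)/2) = √232.685 = 15.254. Standardised difference = 12.4/15.254 = 0.813. At 95% power the noncentral t calculation gives 40.32, rounded up to 41 per arm, which matches the plan. (At 80% power it would be 25; the stated type 2 error of 0.2 conflicts with the stated 95% power, which is a separate matter.) The figure of 50 per arm follows from 41 × 1.2 = 49.2.

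**2. Who is left at week 24.** 50 × (1 − 0.20) = 40 per arm, so about 20 of 100 randomised subjects have no V5 value. Power on the planning effect is 0.948 at 40 per arm against 0.953 at 41. That effect is for hair count, not a primary endpoint, but it shows that lost power is not the issue. Bias is.

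**3. Size of the bias.** The documents give no dropout mechanism and no visit correlation, so both are assumed.

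(a) Simulated trials: 50 per arm, four visits with equal correlation 0.5 to 0.7, about 20% dropout, true effect 0 or 0.5 SD. Dropout depends on earlier observed response in the active arm and is random on placebo. Units are SDs of a single measurement.

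| Analysis of week-24 gloss | Bias in favour of active |
|---|---|
| t-test on change, subjects with V5 | +0.05 to +0.11 SD |
| ANCOVA on baseline, subjects with V5 | +0.03 to +0.05 SD |
| Likelihood analysis, all gloss visits | about 0 |
| Any of these, same mechanism in both arms | about 0 |

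A separate run with about 17 to 20% dropout and a logistic slope of −1 gave +0.03 to +0.07, +0.02 to +0.04, and within 0.003 of zero for the first three rows. With the same mechanism in both arms it gave at most 0.02 for any method.

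(b) Large-sample check with unequal dropout rates: dropout depends on the week-16 change (logistic slope −1 per SD) in both arms, and there is no true effect. Here the correlation is between week-16 and week-24 change, and units are SDs of change.

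| Dropout active / placebo | Bias, corr. 0.5 | Bias, corr. 0.7 | Using week-16 values |
|---|---|---|---|
| 20% / 20% | 0.00 | 0.00 | about 0 |
| 25% / 15% | 0.04 | 0.06 | about 0 |
| 30% / 10% | 0.08 | 0.11 | about 0 |

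**4. What that bias means.** With 40 per arm and correlation 0.5:
- Change t-test: variance of change = 2(1 − 0.5) = 1, so SE = √(1 × 2/40) = 0.224 SD.
- ANCOVA: residual variance = 1 − 0.5² = 0.75, so SE = √(0.75 × 2/40) = 0.194 SD.

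Bias/SE for ANCOVA = 0.03/0.194 = 0.155 to 0.05/0.194 = 0.258. Two-sided type I error = Φ(−1.96 + δ) + Φ(−1.96 − δ), where δ is that ratio. It gives 5.3% to 5.8%. For the change t-test, 0.05/0.224 = 0.22 to 0.1/0.224 = 0.45 gives about 5.6% to 7.3%.

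**5. Where precision comes from.** At correlation 0.5 the simulated SEs were 0.222 (change t-test), 0.195 (ANCOVA, subjects with V5) and 0.194 (all gloss visits). The gain is from baseline adjustment; weeks 8 and 16 add almost nothing to it.

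**6. If dropout depends on the value that was never recorded** (active arm only):

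| Visit correlation | Change t-test | ANCOVA | All visits |
|---|---|---|---|
| 0.5 | 0.146 | 0.096 | 0.082 |
| 0.7 | 0.083 | 0.065 | 0.051 |

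The all-visit analysis then removes less than half of the change-score bias and little beyond what ANCOVA removes.

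**The case against.** Several points count against a strong version of this concern.

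- **A later SAP is promised.** Section 8 defers implementation, and nothing in section 8.2 forbids imputation. That stands: dropping subjects without V5 is the default that follows from silence, not a stated rule. The deferral does not fill the gap, because the SAP is to build on the protocol's main features and these include no missing-data strategy.
- **The FAS need not equal the PPS.** A reader might infer that the FAS shrinks to the PPS. The documents do not support this. Subjects who stopped product, had a major deviation or failed an entry criterion but attended V5 could enter the FAS and not the PPS. How many there would be cannot be known from the documents.
- **The bias depends on asymmetry.** The trial is double-blind, and nothing in the documents says that poor responders would leave one arm more than the other. This stands; the figures are illustrations, not predictions.
- **ANCOVA is already listed.** A reader might credit the repeated-measures model with the fall in SE from 0.22 to 0.19 SD. Step 5 shows that ANCOVA alone delivers it.
- **Near-zero bias is built in.** It follows from assuming that dropout depends only on recorded values. Step 6 shows what happens otherwise, so a sensitivity analysis is needed.
- **Elasticity gains little.** It has no interim values, and imputing it from gloss relies on a correlation that the documents do not give.

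**Conclusion.** The concern holds in a limited form. The FAS is undefined, the PPS has two conflicting definitions, and no method is given for the roughly 20% of subjects expected to lack week-24 data. Unless missing values are handled, the listed tests omit these subjects, and early leavers' gloss at weeks 8 and 16 plays no part in the week-24 gloss comparison.

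Under outcome-related dropout in the active arm only, with visit correlation 0.5 to 0.7, the bias is about 0.03 to 0.05 SD with ANCOVA and roughly 0.05 to 0.1 SD with the change t-test, with somewhat smaller values when dropout depends only weakly on response. It is about zero if the mechanism is the same in both arms. Under missing-at-random, using all gloss visits brings the bias to about zero; under dropout driven by unrecorded values, 0.05 to 0.08 SD remains. Power is barely affected. This should be corrected, but it does not by itself invalidate the design.

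**What to change.** In section 8.2 and the later SAP:

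1. Define the FAS as all randomised subjects by assigned arm, and keep only the restrictive definition for the PPS.
2. Make the FAS the main efficacy set and the PPS supportive. Otherwise the main result still excludes those who stopped product, and a longitudinal model has little to recover.
3. Gloss: a mixed model for repeated measures on weeks 8, 16 and 24, with baseline gloss, arm, visit and arm-by-visit, estimating the week-24 difference.
4. Elasticity: name baseline-adjusted ANCOVA as the single primary method. Multiple imputation that includes gloss is optional, since its value depends on an unknown correlation.
5. Add a simple missing-not-at-random sensitivity analysis, such as a delta adjustment of the missing week-24 values.

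The cost is wording and a little more programming, with no new visit, measurement or subject. The downside is reliance on missing-at-random for the gloss model. That is a weaker assumption than the one behind comparing only subjects with V5 data, and item 5 tests it.

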# 5. Study setting and design

This randomized controlled study will be conducted at the Korean skin research center(KSRC) in South Korea.

This will be a 24-week, randomized, double-blind, parallel group, placebo-controlled trial with two arms, as summarized below:

- Arm 1 (Placebo arm): placebo; 300 mg capsule twice a day
- Arm 2 (Test group 1): Keranat™; proso millet and wheat extract; 150 mg/capsule twice a day

Study subjects who voluntarily consent to the study at visit 1 (week 0) will be judged for eligibility according to inclusion and exclusion criteria. Selected subjects will be randomly assigned to study groups and tested for functional biomarkers after ingesting the experimental or control foods for 24 weeks.

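### Section 8.2 assigns the between-group comparison of change to a paired t-test, which cannot compare two arms, and does not say which of three valid tests is primary

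*Combined protocol and SAP*

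**What the plan says.** Section 5 sets the design: "This will be a 24-week, randomized, double-blind, parallel group, placebo-controlled trial with two arms". Section 8.1 gives the null hypothesis as equal means in the test and control groups and says that "a primary comparison will be conducted between the placebo arm and the test arm". Section 2.2.1 defines both primary endpoints, hair elasticity and hair gloss, as changes to week 24; the first reads "The change of hair elasticity: Change of the week 24 from baseline".

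The tests are in the last bullet of section 8.2, in this order:

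- "Tests of normality will be performed to evaluate the data distribution". No test, threshold or consequence is given.
- "Test group of continuous variables will be compared to the placebo group using Independent T", continuing after a line break with "test, analysis of covariance, and the Wilcoxon rank-sum test". No primary test and no ANCOVA covariate is named.
- "Comparison between groups according to changes in time will be analyzed using Paired T-test".

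Tests are two-sided at 0.05. The opening of section 8 promises an SAP, to be written after the protocol and finalized before unblinding, and says of it: "These specifications will detail the implementation of all statistical analyzes planned according to the main features reported in the protocol".

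**The concern.** There are two separate problems.

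First, a paired t-test needs two measurements on the same subject. In this trial it can compare week 24 with baseline within an arm, but it cannot compare arms, because Keranat and placebo subjects are not paired. As written, the sentence gives the between-group comparison of change, which is what both primary endpoints are, to a test that does not address the hypothesis in section 8.1. If it were followed, each arm would have its own p-value, and a change on Keranat could be reported as efficacy when placebo changed just as much.

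Second, the three valid tests are joined by a plain 'and'. They can give different p-values on the same data. With no primary test named, the primary result depends on which one is reported. The normality tests hint at a choice between the t-test and Wilcoxon, but no rule is stated, and such a rule would not say where ANCOVA belongs.

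**Working it through.** **1. The plan's own figure: which test does the sample size presume?**

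Inputs from section 8.1: changes of 16.9 ± 15.6 (test) and 4.5 ± 14.9 (control), alpha 0.05, stated power 95%, 1:1 allocation.

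- Difference: 16.9 − 4.5 = 12.4
- Pooled SD: √[(15.6² + 14.9²)/2] = √232.685 = 15.25
- Standardized difference: 12.4/15.25 = 0.813
- Noncentrality for a two-sided independent t-test: 0.813 × √(n/2), with 2n − 2 degrees of freedom
- Power: 0.948 at n = 40 and 0.953 at n = 41 per arm

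So 41 per group reproduces as a two-sided independent t-test at 95% power. (At 80% power the same inputs give 25 per group.) The sample size therefore presumes an unpaired comparison, in conflict with the paired sentence. It is based on hair count, a secondary endpoint (section 2.2.2), and does not settle the analysis of elasticity or gloss.

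**2. Within-arm tests read as efficacy**

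Assume n = 41 per arm and the same true standardized change δ in both arms, so there is no treatment effect. Let p be the chance that one arm's paired t-test is significant (noncentral t, noncentrality δ√41, 40 degrees of freedom, two-sided 0.05). The arms are independent, so the chance that Keranat is significant and placebo is not equals p(1 − p), with a mathematical maximum of 0.25.

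| δ | p | p(1 − p) |
|---|---|---|
| 0 | 0.050 | 4.75% |
| 0.2 | 0.240 | 18.2% |
| 0.302 | 0.471 | 24.9% |
| 0.4 | 0.705 | 20.8% |
| 0.5 | 0.878 | 10.7% |
| 0.6 | 0.963 | 3.6% |

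The value 0.302 is the placebo change assumed in section 8.1, 4.5/14.9. It is illustrative only: it concerns hair count, and the documents give no figures for elasticity or gloss. If the Keranat arm alone were considered, the relevant column is p, which is 47% at that value. In a simulation of the same case the independent t-test rejected in 5.0% of trials.

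**3. Open choice among the three valid tests**

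Simulation under no treatment effect: n = 41 per arm, normal data, equal SD at baseline and week 24, baseline-to-week-24 correlation ρ (assumed; the documents give none). The t-test and Wilcoxon are applied to change, and ANCOVA adjusts for baseline. Type I error per endpoint:

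| Rule | ρ = 0.3 | ρ = 0.5 | ρ = 0.7 |
|---|---|---|---|
| Best of the three (40,000 runs) | 8.6% | 8.0% | 7.5% |
| Best of the three (20,000 runs) | 8.1% | 8.0% | 7.5% |
| Assumed gate: t-test if Shapiro-Wilk p > 0.05 in both arms, else Wilcoxon | 4.9% | 5.2% | 5.0% |
| Better of the gated test and ANCOVA | 7.5% | 7.4% | 6.9% |

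ANCOVA fixed as the only test gives 4.7–5.0%. The excess comes mainly from leaving ANCOVA available as an alternative, not from a choice between t-test and Wilcoxon.

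**4. What the choice costs in precision**

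With equal SDs σ, each subject contributes variance 2σ²(1 − ρ) for change and σ²(1 − ρ²) after ANCOVA adjustment. The ratio is (1 + ρ)/2, or 0.65, 0.75 and 0.85 at ρ = 0.3, 0.5 and 0.7. The unadjusted t-test is valid but less precise. If Wilcoxon were primary, the section 8.1 inputs would need about 43 rather than 41 per group (normal data, relative efficiency 3/π).

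**The case against.** The strongest reply is that the paired sentence is a slip for change over time within each arm. The sentence before it already gives the test-versus-placebo comparison to valid tests, section 8.1 states a between-arm null hypothesis, and 41 per group comes from an unpaired test. A statistician could not run a paired test across two independent arms and would read it as within-arm. On this view the 25% describes a reading of results that the plan nowhere adopts, at a placebo change taken from a secondary endpoint. This is a likely account of the intent, and it limits the weight of the first problem. It does not correct the text, which still says the comparison is between groups.

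On the test list, the 'and' may mean that all three tests will be reported. If all three had to be significant, type I error would be 1.9%, 2.2% and 2.8% at ρ = 0.3, 0.5 and 0.7, below 5%. A normality gate would hold it near 5%. This stands: 7.5–8.5% is a worst case. But the plan states none of these rules, and the error rate runs from about 2% to over 8% depending on which is applied.

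Finally, section 8 defers detail to an SAP fixed before unblinding. This is the best mitigation, and it would close the second problem if that SAP names one test. However, that SAP is to follow the protocol's main features, which include the faulty sentence and the unordered list, and the supplied text contains no fuller plan.

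It is also true that ANCOVA is a preference: naming any one of the three valid tests would remove the ambiguity.

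**Conclusion.** The concern holds and should be fixed before unblinding. The paired sentence is wrong as written for a two-arm parallel trial, and no other section corrects it. The plan does contain valid between-arm tests, so the defect is a contradictory instruction plus an open choice, not the absence of a usable analysis.

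The two sizes are conditional. The range of 4.75% to 25% applies only if within-arm significance is taken as efficacy, and its position in that range for elasticity or gloss is unknown. The rise from 5% to about 7.5–8.5% per endpoint applies only if the most favourable test is chosen freely, and rests on normal data and an assumed ρ of 0.3–0.7. Confidence in the textual finding is high.

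**What to change.** In section 8.2 and in the SAP, before unblinding:

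- Name one primary between-arm analysis for each primary endpoint. The suggestion is ANCOVA of the week-24 value (or the change) with treatment and the V1 baseline value as terms, two-sided, reporting the adjusted difference and its 95% confidence interval.
- Make the independent t-test and Wilcoxon rank-sum test sensitivity analyses that do not replace the primary analysis, whatever the normality tests show.
- Reword the paired t-test sentence so that it covers only description of change within each arm, and state that it does not support efficacy claims.

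The cost is wording only. The schedule in section 6 already has elasticity and gloss at V1 and V5, so no visits, measurements or subjects are added.
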